7.1 ADVERSE EVENTS SAFETY ASSESSMENTS	17
8. STUDY MANAGEMENT.....	17
8.1 INSTITUTIONAL REVIEW BOARD (IRB) APPROVAL AND CONSENT	17
8.2 REGISTRATION PROCEDURES	18

8.3	DATA MANAGEMENT AND MONITORING/AUDITING.....	18
8.4	ADHERENCE TO THE PROTOCOL	18
8.5	EMERGENCY MODIFICATIONS.....	18
8.6	PROTOCOL DEVIATIONS/VIOLATIONS	19
8.7	AMENDMENTS TO THE PROTOCOL	19
8.8	RECORD RETENTION	20
8.9	OBLIGATIONS OF INVESTIGATORS	20
8.10	CONFLICT OF INTEREST	20
9.	PLANS FOR PUBLICATION	20
10.	REFERENCES	21
11.	APPENDIX.....	23

PROTOCOL SYNOPSIS

Study Title	Evaluation of Endometriosis with 18F-fluoroestradiol PET / MRI
Funder	The University of North Carolina
Clinical Phase	Pilot Study
Study Rationale	Current techniques to diagnose endometriosis (apart from laparoscopy) lack the necessary sensitivity to detect the disease. As endometriosis expresses estrogen receptors, a radiotracer that binds to estrogen receptors may be able to detect it in a noninvasive fashion.
Study Objective(s)	The primary objective is to evaluate the sensitivity and specificity of 18F-fluoroestradiol (FES) PET/MR for evaluating endometriosis. Secondary objectives include comparing PET to conventional MRI, using histopathology from laparotomy as the gold standard and evaluating association of uptake values (SUV-max) with EHP-30 and pain rating scales, controlling for covariates.
Investigational Drug	This study will be an evaluation of the radiotracer, FES, which binds to estrogen receptors and has previously been used to study estrogen receptor expression in tumors, to detect endometriosis.
Study Design	This is a prospective, one arm, single center study of 12 subjects with clinically suspected endometriosis to demonstrate FES PET-MR's clinical utility for diagnosis of endometriosis.
Subject Population key criteria for Inclusion and Exclusion:	Inclusion Criteria 
• Age 18 or older• Clinically suspected endometriosis.• Scheduled for planned operative laparoscopy with no hormone treatment for at least two cycles (Note: if women are amenorrhoeic, 56 days will be used as a substitute for 2 cycles.)• Able to provide informed consent

Exclusion Criteria

- Male patients
- Patients under 18
- Institutionalized subject (prisoner or nursing home patient)
- Patients with known endometrial, breast, or ovarian cancer.
- Pregnant or breast-feeding women
 - Contraindication to MRI (pacemaker, metallic implants, metallic fragments or foreign bodies, body piercings that are unable to be removed, and certain cardiac devices) Subjects will be screened for any contraindications prior to the MRI.
 - Claustrophobia that would prevent subjects from being inside the MRI scanner for the duration of the scan.

Number Of Subjects	A total of 12 participants will be recruited from individuals with clinically suspected endometriosis.
Study Duration	This study is anticipated to last approximately 1 year.
Statistical And Analytic Plan	The sensitivity of FES PET /MR is defined as the ability of readers (radiologists) to detect endometriosis in patients. Diagnostic accuracy will be defined by the histologic presence of endometriosis and by symptomatic improvement as defined clinically by the referring physician within 3 months of surgery.
DATA AND SAFETY MONITORING PLAN	The Principal Investigator will provide continuous monitoring of patient safety in this trial with periodic reporting to an independent Medical Monitor.

1. BACKGROUND AND RATIONALE

1.1 Introduction

Endometriosis is a major cause of infertility and pain for many women of childbearing age. Estimates of the frequency of endometriosis in infertile women range from 20-50%, with an estimated overall prevalence of 0.8-6% in the female population.¹

Imaging is often used for evaluation of endometriosis. Endometriosis is divided by location into ovarian, peritoneal, and deep; ovarian endometriosis is located in the ovary (often known as endometrioma), peritoneal endometriosis is in the peritoneum penetrating less than 5 mm, and a deep infiltrating endometriotic (DIE) lesion penetrates into the retroperitoneal space or pelvic organ walls to at least 5 mm, affecting 4-37% of women with endometriosis. Transvaginal ultrasound is usually the first-line imaging modality used, with MRI as a second line to look for deep implants.² In general, these are both quite effective, with transvaginal ultrasound being effective for genital DIE and MRI for the diagnosis of pelvic genital and extragenital DIE; however, even MRI can have difficulty distinguishing between surgical scar and active lesions if the patient has been previously operated, and questions still remain about its efficacy in evaluating nerves and bowel.³

While DIE is often amenable to detection by conventional methods, more superficial lesions, even those with extensive coverage of the pelvic endometrium, are frequently invisible to currently-used imaging techniques.⁴ The lack of non-surgical diagnostic or even screening tests is one factor leading to the average five to nine-year delay between symptom onset and diagnosis.^{5,6} The ability to detect earlier-stage endometriosis could play a key role in preventing unnecessary surgery on the one hand and prevention of progression on the other.⁷ The overlap in symptoms between endometriosis and other causes of chronic pelvic pain also makes recurrence difficult to assess, leading to potentially preventable repeat surgery.⁷ Finally, without non-surgical diagnostic techniques, innovations in medical therapy are very difficult to develop. These factors have led to an international consensus that non-invasive diagnostic testing is a key research priority for the field.⁷

One potential option for imaging endometriosis is a radiotracer, 16α -[^{18}F]fluoro- 17β -estradiol or more commonly ^{18}F -fluoroestradiol (FES). This involves an estradiol molecule which has been labeled with a radioactive fluorine atom, which binds to estrogen receptors and can be detected by positron emission tomography (PET). The tracer correlates with receptor expression in biopsy material^{8,9}, and can be administered with minimal (<50 micrograms) estrogenic material¹⁰ and doses similar to those in other nuclear medicine studies.¹¹⁻¹³ This tracer has already been demonstrated for use with estrogen-receptor positive breast, endometrial, and ovarian cancers, correlating with expression in tumors, response to endocrine therapy, assessment of tumor burden and heterogeneity of disease, and pharmacodynamics.¹⁴ Other applications have included differentiating endometrial hyperplasia from endometrial cancer and differentiating

benign uterine leiomyomas from malignant uterine sarcomas.¹⁴ Given that endometriosis contains estrogen receptors, we hope to use FES to identify endometriosis using non-invasive imaging approaches.

1.2 Existing work with FES

Current use of FES: At the present time, FES has only been used to find endometriosis in one study of 4 patients with extragenital endometriosis, specifically of the deep infiltrating variety. This study showed multiple lesions detectable on FES-PET that were not detectable on MRI; of the 9 lesions found by histology, 4 were found by MRI, 8 by FES-PET, and the histology agreed with PET in all cases.³ There was also a limited relationship between SUVmax and chronic pelvic pain.³ Furthermore, this study was performed using PET/CT, which increases the radiation exposure to patients relative to PET/MR.

Our innovation: Previous work with FES has involved breast cancer or other malignancies which express estrogen receptors, such as endometrial cancer. We are hoping to build on prior work by Cosma et al.³ which shows that endometriosis, which also displays endometrial receptors, can be detected by FES-PET.

In addition, we will utilize PET/MR rather than PET/CT, to allow us to avoid the radiation dose associated with the CT. This is particularly important in women of childbearing age. In addition, the superior soft tissue contrast of MRI vis-à-vis CT can help to localize lesions in the pelvis. Furthermore, we will utilize novel MR imaging approaches to potentially enhance the sensitivity of MR-only studies to endometriosis. Utilizing PET/MR will also improve the co-registration for the development of MR based approaches. If endometriosis could be reliably detected through noninvasive imaging, infertility patients who did not display FES uptake, particularly those with prior surgical history who might be difficult to stage using MRI, could avoid the expense and pain of exploratory laparotomy.

2. STUDY OBJECTIVES

The aim of this study is to demonstrate FES PET/MR's clinical utility for diagnosis of endometriosis.

2.1 Primary Objectives

Aim 1: The primary objective is to evaluate the sensitivity and specificity of FES PET/MR for evaluating endometriosis.

2.2 Secondary Objectives

Aim 2: To compare PET to conventional MRI, using histopathology from laparotomy as the gold standard.

Aim 3: To evaluate the association of uptake values (SUV-max) with EHP-30 and pain rating scales, controlling for BMI, race, age, and physician.

3. INVESTIGATIONAL PLAN

3.1 Study Design

This is a prospective, one arm, single center study of 12 subjects with clinically suspected endometriosis to demonstrate PET-MR's clinical utility for diagnosis of endometriosis.

3.2 Study Duration, Enrollment and Number of Subjects

We will include a total of 12 participants in this trial. These subjects will be followed for up to 3 months after initial imaging with PET-MR.

3.3 Study Population

3.3.1 Inclusion Criteria

- Age 18 or older
- Female of childbearing age
- Clinically suspected (symptomatic) endometriosis.
- Scheduled for planned operative laparoscopy with no hormone treatment for at least two cycles (Note: if women are amenorrhoeic, 56 days will be used as a substitute for 2 cycles.)
- Able to provide informed consent

3.3.2 Exclusion Criteria

- Male
- Institutionalized subject (prisoner or nursing home patient)
- Known history of breast, ovarian or endometrial cancer.
- Pregnant or breast-feeding women
- Contraindication to MRI (pacemaker, metallic implants, metallic fragments or foreign bodies, body piercings that are unable to be removed, and certain cardiac devices) Subjects will be screened for any contraindications prior to the MRI.
- Claustrophobia that would prevent subjects from being inside the MRI scanner for the duration of the scan.

4. STUDY PROCEDURES

Patients with suspected (but not confirmed) endometriosis and suspicion of extragenital DIE who are scheduled for planned operative laparoscopy with no hormone treatment for at least two cycles will be recruited from the Minimally Invasive Gynecological Surgery Clinic (Director, [name], Co-I) at UNC. If women are amenorrhoeic, 56 days will be used as a substitute for 2 cycles. The Endometriosis Health Profile-30 (EHP-30), a quality of life questionnaire used in women with endometriosis, a pain numeric rating scale, and information about the last menstrual period will be obtained. Patients will undergo FES PET/MR within 4 weeks prior to surgery. Prior to surgery, suspected areas of endometriosis will be identified on imaging. These imaging findings will then be

compared to surgical findings and histopathology from exploratory laparotomy. Surgical documentation of endometriosis location will rely on published, consensus staging methods.^{15,16} Surgeons will not see the results from the FES-PET/MRI prior to surgery. The results of FES-PET MRI will not be used to guide surgery. The surgeons will be performing exploratory laparoscopy as per standard of care.

4.1 Screening/Baseline Visit procedures

A total of 12 participants will be enrolled to this study. The study subjects will be consecutively recruited from individuals that have clinically suspected endometriosis and have planned exploratory laparoscopy. Eligible patients will be identified by research staff review in coordination with the UNC MIGS group.

Once a patient has been referred, the patient will be approached by a coordinator from Radiology to assess interest in participation.

All eligible participants who agree to participate in the study will be asked to come to their scheduled appointment thirty minutes early to complete the informed consent process.

Review of the consent will take place in the privacy of an exam room, or when possible, a sample consent form will be sent to the patient via email prior to the patient's visit to allow for ample review.

Patients will complete the EHP-30 and pain scale questionnaire. In addition, patients will be asked the date of their last menstrual period. These questionnaires may be completed in person, via the phone, or via REDCap, whichever is preferred by the participant.

4.2 Research Imaging Procedure

Participants who consent for the study will be escorted by the research coordinator to the dedicated study room for the imaging exam. For our female patients who are of child bearing age, a pregnancy test will be performed prior to the administration of the radiotracer.

The subject will have the PET-MR scan performed in a similar manner to a conventional clinical PET-MR scans. The imaging agent will be injected approximately one hour prior to imaging after dosimetry and radiotracer has been verified per protocol. The research technologist will assist in positioning the patient in the PET-MR unit. Once positioned, the total scan time is approximately 1 hour. The length of time for the positioning and examination of a subject's pelvis may vary but it is expected that the entire visit will take about 150 minutes. We will not utilize gadolinium contrast agent for this study.

We have extensive experience in the synthesis of radiotracers at the UNC Biomedical Research Imaging Center (BRIC), with dedicated radiochemists and radiopharmacists. We thus expect to be able to synthesize the radiotracer without much difficulty, as there is an established IND available for cross-filing on the NCI website¹⁷, which contains a

full set of manufacturing and QC documents. A manufacturing IND has already been obtained.

4.3 Follow-Up Phone Call

Patients will be called 3 to 4 weeks following the FES PET scan to determine the last menstrual period following the scan.

4.4 Medical Record Abstraction

Participants' medical record will be reviewed for up to 3 months following their initial research imaging to meet the primary aim. The operative surgeon will be asked to fill out a specific post-operative form defining the areas in which they identified visible endometriosis within the pelvis.

4.5 Interpretation

Upon completion of all study image data collection, a reader study will be performed with a fellowship-trained abdominal radiologist and nuclear radiologist (separate individuals). The abdominal and nuclear reads will be performed separately, without discussion between radiologists. MR information will be used for anatomic localization of the PET scan, as is commonly performed. Differences between the two will then be discussed in the eventual publication. All images will be reconstructed using standard algorithms, and nuclear medicine studies presented on MIM workstations for nuclear medicine viewing, with PACS viewing software with conventional zoom/pan/window and level tools. Locations of endometriosis will be recorded with the same classification system as the surgical system. This research classification will be made by radiologists who are blinded to the surgical findings of endometriosis.

4.6 Variables of Interest

Primary Variables of Interest:

- Presence of endometriosis based on imaging (true/false)
- Localization of endometriosis (American Society for Reproductive Medicine Revised Classification of Endometriosis 1997 and World Endometriosis Foundation System)¹⁵
- Standardized Uptake values (positive real number)
- EHP-30 value (integer)
- Pain rating (integer)

5. STATISTICAL CONSIDERATION

5.1 Primary Endpoint

The sensitivity of FES PET /MR is defined as the ability of readers (radiologists) to detect endometriosis in patients. Diagnostic accuracy will be defined by the histologic presence of endometriosis and by symptomatic improvement as defined surgically by the referring physician within 3 months of surgery.

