5.2 Statistical Methods

Subjects will be recruited until 12 subjects complete the research imaging. For subjects that are enrolled and do not complete the research PET/MR, they will be considered a screen fail and replaced. Two radiologists, a nuclear radiologist and an abdominal radiologist, will be recruited to conduct the reader study. Both the radiologists and surgeons will utilize the Revised Endometriosis Classification System.

Sensitivity and specificity of 18F-fluoroestradiol (FES) PET/MR for evaluating endometriosis will be computed by comparing imaging against surgical findings and histopathology in order to answer Aim 1. We will compute point estimates, along with 95% confidence intervals and precision estimates that may be used to plan future studies.

We will address Aim 2 in the following fashion. After imaging, we will compare the PET results against conventional MRI, using histopathology obtained at exploratory laparotomy as the gold standard. We will do this in 2 phases, first, at the patient level, and then, as an ancillary analysis, at the endometriotic implant site level. For each phase, we will report sensitivity, specificity, and accuracy of the PET results, along with associated 95% confidence intervals. We will also report sensitivity, specificity, and accuracy, along with associated 95% confidence intervals, using conventional MRI. We will use McNemar's test, constructing the 2x2 table among all patients with a surgical diagnosis of positive to compare sensitivity for PET versus conventional MRI. Similarly, we will use McNemar's test among all patients with a surgical diagnosis of negative to compare specificity for PET versus conventional MRI. P-values <0.05 for the comparison of sensitivity and specificity will be construed as evidence that sensitivity/specificity differ between PET and conventional MRI. P-values >0.05 will be considered inconclusive.

To evaluate Aim 3, whether uptake values are associated with EHP-30 and pain rating scales, we will implement a random effects linear regression model, modeling SUV-max as a function of EHP-30 and the pain rating, while controlling for patient-level covariates (BMI, race, age). We will include physician as a random effect to account for physician-level correlation. P-values <0.05 for the EHP-30 and pain rating parameter estimates will be taken as evidence of association with uptake values. P-values >0.05 will be considered inconclusive.

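### The primary-endpoint sentence adds post-operative symptom improvement to the definition of diagnostic accuracy, while Section 5.2 computes Aim 1 without it; the two must be reconciled

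*Combined protocol and SAP*

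**What the plan says.** Section 5.1, headed Primary Endpoint, reads: "Diagnostic accuracy will be defined by the histologic presence of endometriosis and by symptomatic improvement as defined surgically by the referring physician", with a limit of 3 months after surgery. The Statistical and Analytic Plan row of the synopsis has the same sentence but refers to "symptomatic improvement as defined clinically by the referring physician within 3 months of surgery". One text has improvement judged surgically and the other clinically. Neither gives a threshold for improvement or a rule for a patient in whom histology and symptoms disagree.

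The sections that describe the comparison leave symptoms out. In Section 5.2, sensitivity and specificity are "computed by comparing imaging against surgical findings and histopathology in order to answer Aim 1". Section 4 describes the same comparison without naming an aim: imaging findings are "compared to surgical findings and histopathology from exploratory laparotomy".

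For Aim 2, Section 2.2 sets the objective "To compare PET to conventional MRI, using histopathology from laparotomy as the gold standard". Section 5.2 repeats that gold standard, but then forms its paired tables by surgical diagnosis, for example "McNemar's test among all patients with a surgical diagnosis of negative to compare specificity for PET versus conventional MRI". It does not define that term.

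**The concern.** Sensitivity and specificity need one rule for which patients have the disease. For the primary aim the plan gives two: one with symptom improvement (5.1 and the synopsis) and one without (5.2).

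Symptom improvement does not belong in such a rule. It reflects how a patient responded to surgery. A patient with histologically proven endometriosis may not improve, and a patient without it may. Neither result says whether disease was there when the scan was done.

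The component also has no planned measurement. The EHP-30 and pain scale are collected before surgery (Sections 4 and 4.1). The call at 3 to 4 weeks asks about the last menstrual period (4.3). The contact 1 day after imaging is a safety check (7.1). The surgeon's form records visible disease (4.4). The record review in 4.4 is tied to the primary aim but names no symptom item.

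The Aim 1 results are meant to supply "precision estimates that may be used to plan future studies". A reference standard left open could be settled after the results are known, and any misclassification would carry into the next study's design.

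**Working it through.** The plan gives no figure for this point. The detectable odds ratio in Section 5.3 belongs to the Aim 2 McNemar comparison, and nothing here depends on it. The calculation below shows direction and rough size only.

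**Inputs**
- 12 patients (Sections 3.2 and 5.3).
- P = 9 histology-positive and N = 3 histology-negative: assumed, because the documents give no prevalence for this cohort.
- Sensitivity se = 8/9: borrowed from the 4-patient study in Section 1.2, where FES-PET found 8 of 9 histologic lesions. That is a lesion-level figure, used here at patient level by assumption.
- True specificity sp = 100%: assumed.
- f = share of histology-positive patients who do not improve: assumed 10%, 30% or 50%, unrelated to the PET result.
- m = number of histology-negative patients who improve: 1, 2 or 3.
- q = share of those m patients who are PET-positive.

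**Reading 1: both components required.** Histology-positive patients who do not improve become reference-negative. There are P·f of them, and PET is negative in a share 1 − se.

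Apparent specificity = (N·sp + P·f·(1 − se)) / (N + P·f)

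- f = 10%: (3 + 0.9 × 1/9) / (3 + 0.9) = 3.1/3.9 = 79%
- f = 30%: (3 + 2.7 × 1/9) / (3 + 2.7) = 3.3/5.7 = 58%
- f = 50%: (3 + 4.5 × 1/9) / (3 + 4.5) = 3.5/7.5 = 47%

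This is a weighted average of sp and 1 − se. It lies below sp exactly when 1 − se < sp, that is, when sensitivity plus specificity exceeds 1. Expected sensitivity stays at se, because improvement is taken as unrelated to PET.

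**Reading 2: either component suffices.** Histology-negative patients who improve become reference-positive.

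Apparent sensitivity = (P·se + m·q) / (P + m)

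| m | PET misses them (q = 0) | PET calls them positive (q = 1) | Reference-negatives left |
|---|---|---|---|
| 1 | 8/10 = 80% | 9/10 = 90% | 2 |
| 2 | 8/11 = 73% | 10/11 = 91% | 1 |
| 3 | 8/12 = 67% | 11/12 = 92% | 0 |

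Against 8/9 = 89%, sensitivity falls if PET misses the reclassified patients and does not fall if PET calls them positive. With 3 improvers no reference-negative patient remains and specificity has no denominator.

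**Reading 3: Section 5.2 as written.** Symptoms play no part and none of these shifts occurs. What remains open is how surgical findings and histopathology combine when they disagree, or when no tissue is taken.

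**The case against.** The strongest reply is that the working analysis is already free of symptoms. Section 5.2 says how Aim 1 is computed, Section 4 agrees, and Aim 2 names histopathology. On that view the 5.1 sentence is a leftover, and the figures above describe a rule nobody would use. Much of this stands: the bias is conditional on 5.1 being followed. But the sentence sits under the Primary Endpoint heading and again in the synopsis, and nothing says that 5.2 takes precedence.

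It may also be said that a 12-patient pilot is imprecise whatever the reference standard. The plan concedes low precision for Aims 2 and 3. That is random error; misclassifying the reference is a separate problem.

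Three stronger readings are tempting, and the documents do not support them.

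- A reader might infer a further defect in the follow-up window, because record review runs to 3 months after imaging, the endpoint to 3 months after surgery, and surgery may follow the scan by up to 4 weeks. Both limits are maxima, an improvement noted early satisfies both, and the issue disappears once symptoms leave the definition.
- A reader might treat imaged patients whose surgery does not happen as a serious gap, since replacement covers only this case: "For subjects that are enrolled and do not complete the research PET/MR, they will be considered a screen fail and replaced". But planned laparoscopy is an entry criterion, and a patient with no reference result cannot enter a two-by-two table under any rule. This is mostly missing detail.
- A reader might conclude that Aim 2 has the wrong gold standard. The documents state histopathology consistently; surgical diagnosis may be shorthand for it.

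**Conclusion.** The contradiction is certain on the text: 5.1 and the synopsis put symptom improvement into the accuracy definition, differ on how it is judged and give no combination rule, while 5.2 leaves it out. It should be fixed because it concerns the reference standard of the primary aim.

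The size of any bias is not certain. It is zero if 5.2 is followed. If both components were required, specificity would be biased down whenever sensitivity plus specificity exceeds 1: from an assumed 100% to between 79% and 47% in the example. If either sufficed, sensitivity would fall only if PET detects the reclassified patients less often than the histology-positive ones, and specificity would rest on fewer patients or none. Prevalence, improvement rates and specificity are assumptions, and the sensitivity is a lesion-level figure. A reader might infer that the reported primary estimates will be biased; the documents do not support that, because the stated computation does not use symptoms.

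Two smaller points survive even if the sentence is deleted: 5.2 does not say how surgical findings and histopathology combine, and Aim 2 uses an undefined term for the strata of its McNemar tables.

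**What to change.** 1. Delete symptomatic improvement from the accuracy sentence in 5.1 and the synopsis. If it is still wanted, report it as a separate descriptive outcome.
2. For Aim 1, state the patient-level reference standard in line with 5.2: histopathology where tissue is taken, positive if any specimen shows endometriosis; otherwise the surgeon's recorded visual finding. Report how many patients were classified by visual finding alone.
3. Add one sensitivity analysis leaving out patients without tissue. More is not needed at this sample size.
4. In Aim 2, replace the surgical-diagnosis wording so that the McNemar tables use the same reference standard as the Aim 2 estimates. Histopathology stays the gold standard unless the sponsor chooses to extend it to unsampled patients; in that case 2.2, 5.2 and the synopsis must say so, since this changes a stated objective.

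**Cost.** Items 1 to 4 are wording in 5.1, 5.2 and the synopsis, with no change to surgery or imaging. The downside is that patients without tissue rest on visual inspection. The analysis in item 3 can introduce selection bias if sampling depends on what the surgeon sees, so it should remain secondary. Any per-site use of the rule would also need the post-operative form to record which sites were sampled; Section 4.4 describes it only as recording areas of visible disease.
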